		Rectal	2,4,5,6,7,8,9	168

24	Biopsy	Colorectal	2,4,8,9	96
		Cervical	2,4,8,9	96
		Vaginal	2,4,8,9	96

Statistical endpoints

To account for heterogeneity in size of biopsies and absolute concentration (e.g., rectal secretions flushed with media during collection) of the samples, IgG- and protein-normalizations for mucosal samples are performed by dividing VRC07-523LS levels (pg/mL) by the total IgG (ng/mL) and protein concentrations (mg/mL), respectively, as following:

- VRC07-523-LS concentration normalized by total IgG (pg VRC07-523LS/ng total IgG):
 - Units: VRC07-523LS units are pg/mL, and total antibody units are ng/mL. Truncate as specified in the Truncation Rule section below.
 - Antibody normalized concentration = truncated observed concentration / truncated total antibody
- VRC07-523-LS concentration normalized by total protein (pg VRC07-523LS/ng total protein):
 - Units: VRC07-523LS units are pg/mL, and total protein units are mg/mL (milligrams per milliliter). To convert mg to ng, first truncate as specified in the truncation rule section below, then multiply total protein by 1×10^6 (1,000,000).
 - Protein normalized concentration = truncated observed concentration / (10^6 x truncated total protein)

IgG-normalizations for serum samples are performed by dividing VRC07-523LS levels (μ g/mL) by the average reference values for total IgG concentrations in serum in the USA (1165 mg/dL), as following:

- VRC07-523-LS concentration in serum normalized by total IgG (pg VRC07-523LS/ng total IgG):
 - Units: VRC07-523LS units are μ g/mL, and total antibody units are mg/dL. Truncate as specified in the Truncation Rule section below, then divided total antibody by 100.
 - Antibody normalized concentration = truncated observed concentration / (10^{-2} x U.S. reference total antibody)

Truncation rules are applied for SMCxPro, serum, total IgG, and total protein data as following:

- SMCxPro truncation: For results under the smaller value of limit of detection (LLoD) and sample type specific limit of quantification (LLoQ), they are truncated at lower limit of quantification (LLoX) / 2 where LLoX is minimum(LLoQ, LLoD)
- serum truncation: Baseline serum concentrations below the lower limit of quantification (LLoQ = 45.7 ng/ml = 0.0457μ g/ml) are replaced with LLoQ/2. No post-baseline concentrations are below the LLoQ.

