- Total IgG truncation: Total IgG (total IgG = Hu IgG1 + Hu IgG2 + Hu IgG3 + Hu IgG4). Any missing subclass will be treated as zero for the purpose of calculating total IgG. If IgG1, IgG2, IgG3, and IgG4 subclasses are all missing for a sample, the sample will be treated as not collected/no sample recovered, and total IgG will be set to NA. Total IgG concentration will be compared to 48 ng/mL; if it is less than 48 ng/mL, the sample will be flagged in the analysis dataset and excluded from the analysis without truncation.
- Total protein truncation: Compared total protein concentration to 0.167 mg/mL, which will be the last curve point and considered as the LLoQ. If concentration < 0.167 mg/mL, then it will be truncated as $0.5 * 0.167$ mg/mL

Body-weight adjustment will be performed by dividing the IgG- and protein-normalized VRC07-523LS levels by the body weight at baseline. Dose-amount adjustment will be performed by dividing the IgG- and protein-normalized VRC07-523LS levels by the body weight at baseline multiplied the dose amount of the products (T1: 10 mg/kg VRC07-523LS, T2: 30 mg/kg VRC07-523LS). The % penetration into different mucosal compartments will be calculated as the protein-normalized VRC07-523LS level in each of the mucosal specimen type divided by that in serum, multiplied by 100.

Pre-treatment participants and all secretion samples deemed hemoglobin-contaminated or unreliable (1. Total IgG concentration < 48 ng/mL, or 2. Total protein concentration < 0.167 mg/mL, with total IgG concentration also < 48 ng/mL) are excluded from the analysis.

Statistical methods

Tabular summaries of the distributions of body-weight-adjusted, IgG- and protein-normalized VRC07-523LS levels, and % penetration of protein-normalized VRC07-523LS is presented by specimen type, treatment arm, sex at birth and visit. Body weight comparisons between treatment arms (T1 vs. T2) and between sexes at birth (Female vs. Male) are presented using the Wilcoxon Rank Sum Test. A table of partial Spearman's rank correlation coefficients of specimen comparison and p-values, adjusted for treatment group (T1 vs. T2) and sex at birth (males vs. females), is presented by visit. P-values are adjusted for multiple comparisons by controlling the false discovery rate (FDR) using the Benjamini-Hochberg procedure [9] and the q-value [10]. Results are significant if the adjusted p-value or q-value ≤ 0.05 .

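### In SAP 8.3 the low-protein exclusion for secretions removes no sample, so secretions with unquantifiable protein but adequate IgG enter % penetration with a fixed imputed divisor

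*SAP*

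**What the plan says.** All the rules are in SAP 8.3, under Statistical endpoints.

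- **Purpose of normalizing.** Levels are divided by total IgG or total protein to allow for differences in biopsy size and in "absolute concentration (e.g., rectal secretions flushed with media during collection) of the samples".
- **Exclusion of secretions.** A secretion is excluded if it is "hemoglobin-contaminated or unreliable (1. Total IgG concentration < 48 ng/mL, or 2. Total protein concentration < 0.167 mg/mL", and the second criterion carries a further condition on IgG: "2. Total protein concentration < 0.167 mg/mL, with total IgG concentration also < 48 ng/mL) are excluded from the analysis".
- **Low IgG.** Below 48 ng/mL, "the sample will be flagged in the analysis dataset and excluded from the analysis without truncation". If all four IgG subclasses are missing, "the sample will be treated as not collected/no sample recovered, and total IgG will be set to NA".
- **Low protein.** The rule is "Compared total protein concentration to 0.167 mg/mL, which will be the last curve point and considered as the LLoQ". It continues: "If concentration < 0.167 mg/mL, then it will be truncated as" half of that value. The sample is kept.
- **Penetration.** "The % penetration into different mucosal compartments will be calculated as the protein-normalized VRC07-523LS level" in the mucosal specimen over that in serum, times 100. Total IgG does not enter this formula.

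**The concern.** The SAP sets out a protein reliability criterion, but as worded it has no effect. The two divisors are then treated in opposite ways. A sample whose IgG divisor is below its limit is dropped. A secretion whose protein divisor is below its limit, but whose IgG is adequate, is kept with a constant in place of the measurement.

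Half-limit substitution is familiar for a measured analyte. In a denominator whose job is to correct for dilution, a constant switches that correction off for the samples that receive it.

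At stake are the protein-normalized summaries and the % penetration tables in SAP 8.3.1. Those tables test penetration between visits, arms, sexes and specimen types. They include rectal secretions against cervicovaginal secretions and against semen, so a specimen type that the SAP itself describes as flushed is set against others. Paired tests may run on as few as 3 data points and unpaired tests on 5, so one or two imputed divisors could change a result. The false-discovery-rate adjustment does not address this kind of error.

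**Working it through.** The plan states no figure to reproduce here. The check is set logic followed by the effect of the imputed divisor.

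**Inputs (SAP 8.3):** IgG cut-off 48 ng/mL; protein limit 0.167 mg/mL; imputed protein 0.5 × 0.167 = 0.0835 mg/mL (83,500 ng/mL); protein-normalized level = drug level / (10⁶ × truncated protein).

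**Step 1: what the second criterion removes.** Let A = {IgG < 48} and B = {protein < 0.167}. Criterion 1 is A and criterion 2 is A and B. Then A or (A and B) = A, so criterion 2 adds nothing. A truth table across both cut-offs and 1,000,000 simulated IgG/protein pairs each gave 0 samples removed by criterion 2 alone. Missing IgG adds none, because such samples already count as not collected.

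**Step 2: the four cells for a secretion.**

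| | Protein ≥ 0.167 | Protein < 0.167 |
|---|---|---|
| IgG ≥ 48 | kept, measured divisor | kept, divisor fixed at 0.0835 |
| IgG < 48 | excluded | excluded |

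**Step 3: size of the error in the upper right cell.** Reported / true = true protein / 0.0835. Serum protein (SAP reference 70 g/L, that is 70 mg/mL) is far above the limit, so the factor passes unchanged into % penetration. The true protein values below are assumptions, since the documents give no distribution.

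| True protein (mg/mL) | Reported / true |
|---|---|
| just under 0.167 | 2.00 |
| 0.16 | 1.92 |
| 0.12 | 1.44 |
| 0.0835 | 1.00 |
| 0.04 | 0.48 |
| 0.02 | 0.24 |
| 0.01 | 0.12 |

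At 0.167 the ratio returns to 1.00, so there is a 2-fold jump at the limit. Two secretions with the same true normalized level, one diluted eightfold more than the other (0.16 against 0.02), would be reported eightfold apart (1.92 / 0.24 = 8), provided both have IgG of at least 48 ng/mL.

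**Step 4: can the IgG criterion stand in for a protein criterion?** At the protein limit, IgG of 48 ng/mL is 48 / 167,000 = 0.029% of protein by mass. The SAP's serum references (1165 mg/dL IgG, which is 11.65 g/L, and 70 g/L protein) give 11.65 / 70 = 16.6%. The mucosal ratio is not given, so a range is shown:

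| Assumed IgG:protein ratio | Protein at which IgG reaches 48 ng/mL | Fold below 0.167 |
|---|---|---|
| as in serum | about 0.0003 mg/mL | about 580 |
| one-tenth of serum | about 0.003 mg/mL | about 58 |
| one-hundredth of serum | about 0.029 mg/mL | about 5.8 |

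Across this range, protein falls well below its limit before the IgG criterion acts.

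**The case against.** **The redundancy changes no result by itself.** This stands. The imputed divisor comes from the truncation rule, which is openly stated. A reader might infer that the logic slip causes the imputation. It does not: the slip only means that nothing removes those samples first.

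**The most dilute secretions are already handled.** This stands for samples low on both measures, which the IgG criterion excludes. A reader might infer that dilute samples in general are mishandled. The documents support this only for low protein with adequate IgG.

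**The documents do not show that low-IgG samples with valid protein are wrongly lost.** A reader might take the lower left cell in Step 2 as a second error, because IgG plays no part in penetration. But VRC07-523LS is itself an IgG, and the SAP calls such secretions unreliable, so the cut-off may be a deliberate quality gate on the numerator. The cell also needs IgG below about 0.03% of protein at the limit, and less at higher protein. The two criteria may instead have been meant for separate endpoints. The SAP joins them without that restriction, so clarification is due, not a finding of loss. Even on the endpoint reading, the fixed divisor would remain for low protein with adequate IgG.

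**Materiality is not shown.** Partly stands. The number affected is unknown, values below 0.0835 mg/mL are hypothetical, and rank tests limit the pull of extreme ratios. Ranks can still shift, however, and the cells are small. % penetration is not a named objective or endpoint in Protocol 5.1 or 5.2.

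**Excluding by protein selects on dilution.** True, which is why the truncated result should be shown alongside.

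**Conclusion.** The point holds, within limits. It is certain from the text that the second criterion excludes no additional secretion, and that secretions with protein below 0.167 mg/mL and IgG of 48 ng/mL or more carry a constant divisor of 0.0835 mg/mL. For each such sample the error in the protein-normalized level and % penetration is at most 2-fold upward and has no lower bound downward.

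How much this moves any comparison cannot be computed, because the documents give neither the protein and IgG distributions nor the number of samples in that cell. A reader might infer that the trial's drug-level results as a whole are distorted. The documents do not support that: the IgG-normalized visit, arm and sex comparisons, the regression models and the scatterplot correlations do not use the imputed protein value.

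The rule should be corrected before the penetration tables are interpreted, since it is void as written and the change is small.

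**What to change.** - **Secretions.** For protein-normalized levels and % penetration, exclude samples with total protein below 0.167 mg/mL regardless of IgG. Show the half-limit truncation result beside it as a sensitivity analysis.
- **Counts.** Report the number of truncated-protein samples by specimen type, arm and visit.
- **IgG criterion.** State whether IgG below 48 ng/mL is a general sample-quality gate or applies only to IgG-normalized endpoints. If it is not a quality gate, keep low-IgG samples with quantifiable protein in the penetration analysis, at least as a sensitivity analysis. Align this with the IgG normalization formula, which divides by a truncated total although low IgG is said to be excluded untruncated.
- **Biopsies.** The two-part exclusion names secretions only, while the protein truncation is stated without specimen restriction. Report the truncated-protein counts for biopsies and a sensitivity analysis without those samples. A new primary exclusion for biopsies is not required.

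The cost is one changed filter, a few sentences in the SAP and one added set of tables. The downside is that a few dilute secretions may leave penetration cells that hold at most 12 participants per arm, and about 6 per arm and sex, so some comparisons may fall below the minimum of 3 paired or 5 unpaired points.

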## 6 Statistical considerations

### 6.1 Accrual and sample size calculations

Recruitment will target accruing a total of 24 healthy, HIV-1–uninfected adult participants in two treatment groups, with 12 participants assigned to each group.

In Group 1, all study participants will receive three IV administrations of VRC07-523LS at the 10 mg/kg dose level. In Group 2, all study participants will receive three IV administrations of VRC07-523LS at the 30 mg/kg dose level.

In both groups, the three infusions will be administered every 16 weeks.

Participants will be randomly assigned to either one of the groups. Groups 1 and 2 will open to randomization at the same time.

In Groups 1 and 2, every study participant will be followed for 12 months (including 8 months of product administration plus 4 months of follow-up) from the day of first product administration.

To ensure balance in the trial of both sexes assigned at birth, the trial will enroll at least and approximately 50% of participants assigned female sex at birth. Randomization will be stratified by assigned sex at birth to ensure balance within each treatment group.

The times at which samples will be collected are listed in [Table 9-1](#) and [Table 9-2](#) for each mucosal site and the blood.

Since enrollment is concurrent with the first biopsy sample collection, all participants will provide some data regarding tolerability of mucosal sample collections. For analyses of VRC07-523LS levels in serum and mucosa and of data from ADA assays, it is possible that data may be missing for various reasons, such as participants terminating from the study early, problems in shipping specimens, or high assay background. Immunogenicity data from 17 phase 1 and 2 phase 2a HVTN vaccine trials, which began enrolling after June 2005 (data as of September 2014), indicate that 17% is a reasonable estimate for the rate of missing data. In HVTN 104 (phase 1 trial of VRC01), approximately 10-15% of drug concentration data were missing at the primary timepoints.

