## 9.6 Mucosal sampling

Mucosal secretion and biopsy samples will be collected at the timepoints indicated in [Appendix D](#). All participants in this trial will have consented to mucosal specimen collections. Participants assigned male sex at birth will provide semen, rectal secretions, and rectal biopsies. Participants assigned female sex at birth will provide cervicovaginal and rectal secretions, as well as cervical, vaginal and rectal biopsies. Small (~2-4 mm) tissue biopsies are obtained from the vagina and ectocervix using a speculum and from the rectum by anoscopy by experienced clinicians. The product administration and biopsy collection schedules per mucosal compartment and visit are described in detail in [Table 9-1](#), and also outlined in [Appendix D](#); however, fewer samples may be taken based on the judgment of the performing clinician. The number of biopsies collected per mucosal compartment and visit is shown in [Table 9-2](#). Following the first product administration, a participant may decline all or some of the mucosal biopsies or secretion collections, but they should be encouraged to continue with any collections that they deem acceptable until the end of the trial.

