3.2 Secondary objectives and endpoints

Secondary objective 1:

- To compare dose regimens of VRC07-523LS delivery for their ability to sustain mucosal mAb levels at serial timepoints post repeat administration

Secondary endpoint 1:

- Levels of VRC07-523LS in genital and rectal secretions and tissue at specified timepoints

Secondary objective 2:

- To determine whether ADA can be detected in serum

Secondary endpoint 2:

- Serum concentration of ADA in each group measured at multiple timepoints from baseline through the final study visit

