Preliminary Results are determined using the ELISA Plate Reader (Molecular Devices) SpectraMax i3X absorbance (Hemoglobin) and fluorescence (protein concentration). Assays are assessed for QC using the standards ran on each plate.

The Quant-iT™ Protein Assay Kit (Invitrogen™) is used to measure the total protein in samples provided by study participants. The kit provides concentrated assay reagent, dilution buffer, and pre-diluted BSA standards. Simply dilute the reagent, load it into the wells of a microplate, add 1-20 µL of sample, mix, then measure the fluorescence. The assay is highly selective for protein and exhibits very little protein-to-protein variation. The assay is performed at room temperature, and the signal is stable for 3 hours. Common contaminants, such as salts, solvents, or DNA—but not detergents—are well tolerated in the assay.

Bio-Plex Pro™ Human Isotyping Assay for IgG concentration

The Bio-Plex Pro™ Human Isotyping Assay (Bio-Rad Laboratories, Inc.) is used to measure IgG in mucosal samples provided by study participants. The kit provides magnetic beads, detection antibodies, standards, controls, and reagents for detecting human IgG1, IgG2, IgG3, IgG4, IgA, and IgM. Samples are diluted in the provided kit buffer and mixed with the multiplex magnetic bead panel in a 96-well plate. Plates are washed with the kit-provided wash buffer, and secondary detection antibodies are added per the package insert instructions. Plates are read on a BioPlex 200 instrument to measure Fluorescence Intensity (FI). Mean Fluorescence Intensity (MFI) values are used to quantify isotype concentrations. Sample isotype concentrations are derived from the kit-supplied standard curve.

Specimens

A total of 24 participants and 504 secretion (semen, cervicovaginal, and rectal) samples (168 of each specimen type) will be tested at 7 timepoints (visits 2, 4, 5, 6, 7, 8 and 9) from Groups 1 and 2. A total of 24 participants and 168 serum samples will be also tested at 7 timepoints (visits 2, 4, 5, 6, 7, 8 and 9) from Groups 1 and 2. A total of 24 participants and 288 biopsy (colorectal, cervical and vaginal) samples (96 of each specimen type) will be tested at 4 timepoints (visits 2, 4, 8 and 9) from Groups 1 and 2.

Summary of sample numbers and specimen types proposed for testing is summarized in the table below:

No. of Participants	Specimen Type		Timepoint (visit)	Total no. of samples
24	Secretion	Semen	2,4,5,6,7,8,9	168
		Cervicovaginal	2,4,5,6,7,8,9	168

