Comparisons of dose-amount-adjusted, IgG-normalized VRC07-523LS concentrations between visits (v2 vs. v5, v2 vs. v7, v2 vs. v9, v4 vs. v6, v4 vs. v8, v6 vs. v8) are made using the Wilcoxon Signed-Rank test, and comparisons between sexes at birth at visits 4 and 5 are made using the Wilcoxon Rank Sum test. Additionally, comparisons of body-weight-adjusted, IgG-normalized VRC07-523LS concentrations between treatment arms at visits 4 and 5 are made using the Wilcoxon Rank Sum test. Comparisons are made for the % penetration of protein-normalized VRC07-523LS between visits, and specimen types using Wilcoxon Signed-Rank test; and between treatment arms using Wilcoxon Rank Sum test; and between sex at birth, controlling for treatment arms using Van Elteren Test. Comparisons are conducted between levels normalized using actual total protein concentrations and those normalized using the U.S. reference protein concentration (70 g/L) with treatment arms (T1 and T2) pooled using the Wilcoxon Signed Rank Test. Linear mixed-effect regression analyses are performed modeling natural log-transformed concentrations as a function of time since most recent infusion, sex at birth, and treatment group. Linear regressions are performed modeling the difference between natural log-transformed concentrations between visits adjusting for the difference between number of days since last infusion at compared visits, as well as sex at birth and treatment group. P-values are adjusted for multiple comparisons by controlling the false discovery rate (FDR) using the Benjamini-Hochberg procedure [9]

and the q-value [10]. Results are significant if the adjusted p-value or q-value ≤ 0.05 . Comparisons are conducted for groups with at least 3 data points for paired test and at least 5 for unpaired test.

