- For rectal biopsies, comparison of penetration percentages (protein-normalized VRC07-523LS of mucosal divided by serum) at visit 4, among different sexes, controlling for treatment arms, using Van Elteren Test. P-values will be adjusted for multiple comparisons by controlling the false discovery rate (FDR) using the Benjamini-Hochberg (BH) procedure and the q-value. The unadjusted p-values, BH-adjusted p-values, and q-values will be reported.
- Among females, comparison of penetration percentages (protein-normalized VRC07-523LS of mucosal divided by serum) at visits 4 and 5 for rectal biopsies vs cervical biopsies, rectal biopsies vs vaginal biopsies, cervical biopsies vs vaginal biopsies, and rectal secretions vs cervicovaginal secretions, using Wilcoxon signed-rank test, with treatment arms combined, by visit. P-values will be adjusted for multiple comparisons by controlling the false discovery rate (FDR) using the Benjamini-Hochberg (BH) procedure and the q-value. The unadjusted p-values, BH-adjusted p-values, and q-values will be reported.

- Among males, comparison of penetration percentages (protein-normalized VRC07-523LS of mucosal divided by serum) at visit 4 for rectal secretions vs semen, using Wilcoxon signed-rank test, with treatment arms combined, by visit. P-values will be adjusted for multiple comparisons by controlling the false discovery rate (FDR) using the Benjamini-Hochberg (BH) procedure and the q-value. The unadjusted p-values, BH-adjusted p-values, and q-values will be reported.
- Comparisons for dose-amount-adjusted protein-normalized VRC07523LS levels in serum between actual total protein levels and U.S. reference protein levels (70 g/L) with T1+T2 pooled using Wilcoxon signed rank test, by specimen type and visit. P-values will be adjusted for multiple comparisons by controlling the false discovery rate (FDR) using the Benjamini-Hochberg (BH) procedure and the q-value. The unadjusted p-values, BH-adjusted p-values, and q-values will be reported.
- Analysis of the impact of time since the most recent infusion, sex at birth, and treatment on log-transformed, body-weight-adjusted IgG-normalized VRC07523LS levels across specimen types using a linear mixed-effects model. P-values will be adjusted for multiple comparisons by controlling the false discovery rate (FDR) using the Benjamini-Hochberg (BH) procedure and the q-value. The unadjusted p-values, BH-adjusted p-values, and q-values will be reported.

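### SAP 8.3 mixed model: with no specimen, infusion-number or arm-by-time term, sex can be confounded with specimen, tissue decline can be understated, and decline is not compared between doses

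*SAP*

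**What the plan says.** - **Mixed model.** SAP 8.3, Statistical methods, describes it as "modeling natural log-transformed concentrations as a function of time since most recent infusion, sex at birth, and treatment group". The entry in SAP 8.3.1 applies it to log body-weight-adjusted, IgG-normalized "levels across specimen types using a linear mixed-effects model". The outcome is not divided by dose, so the arm coefficient carries the threefold dose difference.
- **Companion model.** The next sentence of SAP 8.3 reads: "Linear regressions are performed modeling the difference between natural log-transformed concentrations between visits adjusting for the difference between number of days since last infusion". It also adjusts for sex and arm. It does not name the visit pairs.
- **Who gives what.** Protocol 9.6: "Participants assigned male sex at birth will provide semen, rectal secretions, and rectal biopsies". Also: "Participants assigned female sex at birth will provide cervicovaginal and rectal secretions, as well as cervical, vaginal and rectal biopsies". Protocol 6.1 adds that "the trial will enroll at least and approximately 50% of participants assigned female sex at birth".
- **When.** Biopsies, SAP 8.3, Specimens: "288 biopsy (colorectal, cervical and vaginal) samples (96 of each specimen type) will be tested at 4 timepoints (visits 2, 4, 8 and 9". Visit 2 precedes treatment and is excluded. That leaves day 14 after infusion 1, day 14 after infusion 3 and day 112 after infusion 3. Secretions are taken at day 14 and day 112 after every infusion (visits 4 to 9).
- **What the analysis should serve.** Secondary objective 1: "To compare dose regimens of VRC07-523LS delivery for their ability to sustain mucosal mAb levels at serial timepoints post repeat administration".

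**The concern.** Each omitted term has its own consequence.

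1. **Specimen.** Four of the six mucosal specimen types come from one sex only. A pooled model without a specimen term attributes part of any difference between specimens to sex. A model fitted type by type has a constant sex column in those four.
2. **Infusion number.** In tissue the only late sample follows the third infusion, while half of the early samples follow the first. Any accumulation raises the late sample relative to the average early one and flattens the fitted decline.
3. **Arm-by-time.** One common slope cannot show whether one dose holds its level longer than the other.

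At stake are a sex difference that may not exist, a tissue decline that looks too slow, and a secondary objective without a clear between-dose comparison after repeat dosing.

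**Working it through.** **Inputs.** Visit grid and specimen types: SAP 8.3, Protocol 9.6 and Table 9-1. Split of 12 females and 12 males: from the roughly 50% target. Assumed: half-lives, fold differences between specimens, a participant SD of 0.4 and a residual SD of 0.5 on the log scale. The text available gives only macaque half-lives of 9.8 to about 14 days (Protocol 4.2.1) and no human value.

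**The SAP's own counts.** 24 × 7 = 168 per secretion type, × 3 = 504. 24 × 4 = 96 per biopsy type, × 3 = 288. Both reproduce, but only if all 24 participants give every type. At 12/12 the maxima are 84 semen + 84 cervicovaginal + 168 rectal = 336 secretions, and 96 rectal + 48 cervical + 48 vaginal = 192 biopsies. The counts do not reflect that four types are single-sex.

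**Sex, pooled reading.** Post-baseline records per person:
- Female: 6 rectal secretion + 6 cervicovaginal + 3 + 3 + 3 biopsies = 21, of which 12 (57%) are female-only types.
- Male: 6 rectal secretion + 6 semen + 3 rectal biopsy = 15, of which 6 (40%) are semen.

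Suppose there is no sex effect and semen is lower by a factor f. The expected female-minus-male contrast is (6/15)·ln f.
- f = 2: exp(0.4 × 0.693) = 1.32
- f = 3: exp(0.4 × 1.099) = 1.55
- f = 10: exp(0.4 × 2.303) = 2.51

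In 200 simulated trials with semen threefold below and cervicovaginal threefold above rectal, the sex coefficient averaged 0.755 (exp = 2.1-fold). Unadjusted p was below 0.05 in 99%. Adding a specimen term gave 0.000 and 5%. With a true 1.5-fold sex effect (0.405), the model without specimen gave 1.145, which mixes both effects.

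**Sex, per-specimen reading.** The bias disappears. Sex is not estimable in semen, cervicovaginal, cervical or vaginal samples.

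**Tissue decline, fitted to tissue.** Let k be the elimination rate and R the day-14 level after infusion 3 divided by that after infusion 1. The fitted slope is

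[y9 − (y4 + y8)/2]/98 = −k + 0.5·ln(R)/98.

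For one-compartment linear kinetics and a 112-day interval, R = 1 + a + a², with a = 2^(−112/half-life).

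| Half-life (days) | R | Decline understated | Apparent half-life (days) |
|---|---|---|---|
| 12 | 1.002 | 0.0% | 12.0 |
| 40 | 1.164 | 4.5% | 41.9 |
| 60 | 1.349 | 13.2% | 69.2 |
| 90 | 1.600 | 31.1% | 130.7 |

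Example at 60 days: k = 0.693/60 = 0.01155; 0.5 × ln(1.349)/98 = 0.00153; 0.00153/0.01155 = 13.2%. Simulated rectal biopsies at 45 days (true slope −0.0154/day) gave −0.0144 without infusion number and −0.0153 with it. In secretions infusion number is balanced against time, so accumulation alone causes no bias.

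**Arm-by-time.** With half-lives of 30 and 60 days in the two arms, the true slope difference is 0.693/30 − 0.693/60 = 0.0116/day. The written model returns one slope (−0.0168). A day-by-arm term returns 0.0119, and a visit 9 minus visit 8 regression on arm returns 0.0114.

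**Other listed between-arm analyses of mucosal data.** Levels are compared at visits 4 and 5, both after infusion 1, and at peak timepoints. Penetration is compared at visit 4, and for secretions also at visit 5. None covers the troughs at visits 7 and 9. The visit pairs listed for the signed-rank tests are peak-peak or start from visit 2, where time since infusion is undefined. None is peak-trough.

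**The case against.** The strongest reply is that much of this depends on how the SAP is read.

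- **Pooling is not stated.** SAP 8.3 speaks of analyses in the plural, and most level comparisons in 8.3.1 are by specimen type. That stands: the false sex effect arises only if the data are pooled. The two model entries depart from the by-specimen wording, so pooling remains a fair reading.
- **The sex and tissue figures do not describe one fit.** Correct. The sex ratios need a pooled model; the tissue table needs a fit to tissue.
- **Sex is handled well elsewhere.** The SAP's between-sex tests are confined to rectal secretions and rectal biopsies. True; the models simply do not carry that rule over.
- **Half-life is not this model's output.** Protocol 6.4.4.1 assigns half-life, and arm comparisons of kinetic parameters, to exploratory population models. Accumulation is tested directly at visit 4 versus 8. Both stand and limit the harm.
- **The difference regression could compare decline.** It could, if a peak-trough pair were named.
- **Levels are the endpoint.** Secondary endpoint 1 concerns levels at specified timepoints, so the arm term is relevant. It gives an average level difference, about ln 3 (1.10 simulated) when half-lives are equal.

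A reader might also infer that the sex-adjusted partial Spearman table shares the fault. It does not: any pair involving a single-sex specimen contains one sex only, so sex is constant there and cannot confound.

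**Conclusion.** The point holds as a specification defect that should be corrected.

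- **Sex:** confounded with specimen if pooled (false ratio 1.32 to 2.51 for semen 2- to 10-fold lower, assumed); not estimable in four of six mucosal types if fitted separately.
- **Tissue decline:** understated whenever the antibody accumulates, always toward slower decline. The size runs from nil at 12 days to 13% at 60 and 31% at 90, under assumed half-lives, linear kinetics and nominal visit days.
- **Dose comparison:** the model imposes equal decline, and no other listed analysis clearly compares the arms' mucosal decline or later troughs.

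Three stronger readings are not supported. The sex coefficient is not purely a specimen effect, because rectal samples from both sexes carry real sex information. The documents do not establish that tissue half-life will be reported too long. Nor is the plan unable to compare the doses: the arm term compares average levels, and the difference regression could compare decline. The simulated rejection rates use assumed SDs and unadjusted p-values, whereas the SAP controls the false discovery rate.

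**What to change.** 1. State that the model is fitted per specimen type with a participant random effect. If it is pooled, add a specimen term as well.
2. Keep sex only for specimens given by both sexes: rectal secretions, rectal biopsies and, where modelled, serum. This matches the SAP's own between-sex tests.
3. Add infusion number (1 to 3 in secretions; 1 and 3 in tissue).
4. Add an arm-by-time-since-infusion term with a 95% CI, or specify the difference regression on a peak-trough pair such as visit 9 minus visit 8. Name whichever is chosen as the decline comparison for secondary objective 1. The pair has the advantage that both visits follow the same infusion.

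The cost is a few lines of SAP text and a few more parameters. In tissue, decline then rests on visits 8 and 9 alone: the variance factor rises from 1 + 1/2 to 1 + 1, so the standard error grows by √(2/1.5) = 1.15, about 15%. In cervical and vaginal tissue the arm comparison is about 6 against 6, so its interval will be wide and is best read as descriptive.
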